8.2 Key Secondary Outcomes

- Mortality is a key secondary outcome; analyses are described in section 7.
- To supplement the separate analyses of time to sustained recovery and time to death, the two endpoints will be analyzed jointly using the "win ratio" method for the composite outcome of time to recovery or death.⁸ The win ratio will be calculated using the matched pairs method described in Pocock (2012).⁸ Pairs will be formed by ranking the participants in each treatment group according to a risk score, described in section 13.2, and pairing the participants in groups A (here referring to the investigational drug) and B (referring to control) with equal ranks. Details are given below.
 - If both treatment groups have the same number of observations, the win ratio is calculated as follows:

Step 1: Calculate the risk score for all participants, and order participants by the risk score in each treatment group. If needed, break ties at random. Each participant forms a "matched pair" with the participant of equal rank order in the other treatment group.

Step 2: For each pair, determine whether the participant in group A wins, loses, or neither:

- a. Compare pairs for time to death, for all pairs where one or both participants died. If the participant in group A died, wins and losses are computed as follows:
 - If the matched participant in group B has longer follow-up, then A loses and B wins.
 - If the matched participant in group B has shorter follow-up and is alive at the censoring date, then neither group wins.

Repeat for pairs where the participant in group B died.

- b. Compare remaining pairs for time to sustained recovery.
 - If A achieved sustained recovery, and time to sustained recovery is longer for B, then A wins and B loses; vice versa for B.
 - If A achieved sustained recovery, and B was censored without reaching sustained recovery before A reached sustained recovery, then neither group wins; vice versa for B.
 - Otherwise, neither group wins.

Step 3: Calculate the win ratio as the number of wins in group A divided by the total number of pairs with a win or a loss in group A. Calculate the 95% CI for the win ratio and p-value as described in Pocock (2012).⁸

- If one treatment group has more participants than the other, select $|n_A n_B|$ participants at random from the larger group and delete. Calculate the win ratio, 95% CI and p-value for the resulting matched pairs. Repeat the random selection of observations to delete 501 times; identify the matched pairs data set that corresponds to the median win ratio; the final values of the win ratio, 95% CI and p-value are those calculated from this data set.
- If both treatment groups have the same number of observations, but some ranked risk scores are tied within a treatment group, a similar process may be used to repeat the random breaking of ties, with the final win ratio chosen as the median over repeated random tie breaks.

With this approach, time to death is first used to determine the winning group (i.e., longer time to death), then time to sustained recovery is used to determine the winning group (i.e., shorter time to recovery): in this manner, the win ratio combines these conflicting outcomes into a composite while recognizing the importance of mortality.

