13.2 Disease Progression Risk Score

A disease progression risk score, calculated at baseline, will be used to form subgroups of participants with low or high predicted risk for subgroup analyses for safety and efficacy outcomes, and to pair participants for the win ratio analyses described in section 8.2.

The risk score for a participant is defined as the estimated *probability that the Pulmonary outcome on Day 5 is in one of the categories 5, 6 or 7* (5=non-invasive ventilation or high-flow oxygen, 6=invasive ventilation, 7=death). The probability is estimated using a logistic regression model for the corresponding binary outcome (Pulmonary categories \geq 5 vs <5 on Day 5) with the following baseline predictors: age, sex, Pulmonary category at baseline, days since symptom onset, NEW score, and indicator variables for the following risk factors: asthma/COPD, diabetes, CVD, heart failure, hypertension, HIV or other immune deficiency, and renal impairment. The risk score will be derived from the pooled data for the investigational agent/placebo groups. Thus, the risk score will be specific to each investigational agent.

14 Unblinding of Treatment Comparisons

For any investigational agent, trial results will be unblinded when the pre-specified number of primary endpoints is reached; results may be unblinded earlier upon the recommendation of the DSMB if the sponsor and study leadership concur. In this case, trial results for the investigational agent will be unblinded and reported with available data through 90 days of follow-up. After that, data collection will continue as outlined in the data collection plan; under protocol version 3.0, death and re-hospitalizations will be recorded through 18 months.

While the trial is ongoing, access to any data summaries by treatment group (investigational agent or control groups) will be restricted to the members of the DSMB, the DSMB's Executive Secretary, and the unblinded statisticians.

When the trial for an investigational agent is concluded, data for the investigational agent and the corresponding pooled control group will be unblinded and provided to the study team.

The timing of the unblinding of data for one agent may require consideration, if:

- the control group is substantially shared with another agent for which the trial is still ongoing, **and**
- pooled data on treatment outcomes for the ongoing trial are available to investigators.

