Appendix G. Modifications to the Statistical Analysis Plan for MP0420

Investigational Agent

Appendix H5, version 2.0 (09 April 2021) of the TICO protocol describes agent-specific protocol elements for MP0420 which is being developed by Molecular Partners and Novartis. MP0420 is multi-valent DARPin® molecule consisting of 5 DARPin® domains. MP0420 simultaneously and specifically binds to 3 epitopes of the receptor-binding domain of the SARS-CoV-2 spike protein with three different domains and to human serum albumin with two domains.

Analysis Population

Treatment comparisons for efficacy and safety outcomes will be by modified intention-to-treat (mITT). The mITT analysis is restricted to participants who received a complete or partial infusion of MP0420/placebo; participants who did not receive any MP0420/placebo are excluded. The TICO platform protocol specifies ITT for the efficacy analyses "unless otherwise stated", and mITT for safety analyses.

Justification for changing the study population to mITT for efficacy analyses: In the TICO trial of MP0420, 496 participants were randomized (ITT population). Of these, 485 were infused (complete or partial) with MP0420/placebo and 11 were not. Of the 11 participants not infused, 9 withdrew consent prior to infusion. Follow-up data after Day 0 was collected for the 2 participants not infused, but remained consented. Because the treatment assignment was blinded, the risk of bias due to restricting analyses to the mITT cohort is low. With this approach, the risk and benefits of MP0420 will be evaluated in the same population.

Comment: Investigators were unblinded to summaries of the infusion status of participants, pooled across treatment groups. These analyses were included in the open DSMB reports.

Hypersensitivity Events of Special Interest

In October 2021, we were informed of 3 participants who experienced hypersensitivity reactions in a Molecular Partners study of 20 healthy volunteers. The 3 participants received a 400 mg subcutaneous dose of MP0420 and each developed non-serious (mild to moderate) rash and joint/body pain 10 to 20 days after the single subcutaneous infusion. A total of 8 participants received the 400 mg dose in this study.

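### The win-ratio CI and p-value, if based on a pair-level binomial variance, do not describe the rank-paired, median-of-501 estimator; the true level of the nominal 5% test could lie anywhere from about 2% to about 12%

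*SAP*

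**What the plan says.** SAP section 8.2 lists the win ratio as a key secondary outcome that combines death (compared first) with time to sustained recovery.

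- **Pairing.** "Pairs will be formed by ranking the participants in each treatment group according to a risk score". Step 1 pairs each person "with the participant of equal rank order in the other treatment group". There is no caliper and no check on the score distance within a pair.
- **Statistic.** The third step reads: "Calculate the win ratio as the number of wins in group A divided by the total number of pairs with a win or a loss". Wins and losses are those of the investigational arm. This is a proportion with null value 0.5.
- **Inference.** "Calculate the 95% CI for the win ratio and p-value as described in" a cited methods paper. No formula is printed.
- **Unequal arms.** The surplus in the larger arm is deleted at random: "Repeat the random selection of observations to delete 501 times". The data set with the median win ratio is kept, and "the final values of the win ratio, 95% CI and p-value are those calculated from this data set".
- **Score.** Section 13.2 models Pulmonary category 5 or worse on Day 5 from baseline predictors. "The risk score will be derived from the pooled data for the investigational agent/placebo groups". Its prognostic strength is not reported.
- **Numbers.** Appendix G analyses efficacy by mITT. Of 496 randomized, "Of these, 485 were infused (complete or partial"). The split by arm is not given.

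Section 3 says that tests for key secondary outcomes are stratified by disease severity and pharmacy. Section 8.2 does not say how this applies to the win ratio.

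**The concern.** Equal rank within arm is not equal risk. Randomization is stratified by site pharmacy (and later by severity stratum), not by this score, so one arm can by chance be somewhat sicker. Its member at nearly every rank is then the riskier of the pair. All pair probabilities move off 0.5 in the same direction, and the wins are positively correlated. A variance that treats pairs as independent fair coins leaves this out.

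The deletion rule creates a second mismatch in the other direction. The reported estimate is a median over 501 re-pairings, which is more stable than one pairing, yet it carries the CI and p-value of one pairing.

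At stake is whether the 95% CI and the 0.05 threshold of section 3 mean what they say for an analysis intended to reconcile recovery with mortality.

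**Working it through.** **The plan's own figure.** The SAP states no power or error rate for the win ratio beyond the nominal 95% CI and 0.05. The platform's design figure of 843 recoveries reproduces: 4(1.960 + 1.282)²/(ln 1.25)² = 42.04/0.0498, giving 845 by Schoenfeld's formula, with power 0.8996 at 843 events. It concerns the primary test only.

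**Inputs from the SAP.** The pairing, Step 3 and deletion rules of section 8.2; N = 485 from Appendix G; two-sided 0.05 from section 3. The outcome mix is borrowed from Table E-1 (AZD7442): 1195/1417 = 84.3% recovered and 138/1417 = 9.7% died before recovery.

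**Assumptions.** (a) The cited method amounts to z = (W − L)/√(W + L), with W wins and L losses. (b) R² is the share of latent outcome severity that the score explains, varied from 0 to 0.5. (c) The arm split is varied. Unrestricted 1:1 allocation of 485 gives a difference in arm sizes with SD √485 ≈ 22, so differences of 1 to 25 are plausible.

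**Step 1: the omitted component, equal arms.** Let severity be √R²·x + √(1 − R²)·e, with x and e standard normal. A pair with score difference d has its win probability shifted from 0.5 by about 0.399·√R²·d/√(2(1 − R²)). Over n pairs the d's sum to n times the difference in arm means, with variance 2n. The shared shift therefore adds 0.159·n·R²/(1 − R²) to the variance of the win count. Dividing by the binomial n/4:

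variance inflation = 1 + 0.64·R²/(1 − R²).

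The n cancels, so a larger trial does not cure it.

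| R² | Inflation | Approximate size | Simulated, 240/arm | Simulated, 500/arm |
|---|---|---|---|---|
| 0.1 | 1.07 | 5.8% | 6.1% | 5.5% |
| 0.2 | 1.16 | 6.9% | 7.2% | 7.0% |
| 0.3 | 1.27 | 8.3% | 8.8% | 8.2% |
| 0.5 | 1.64 | 12.6% | 12.6% | 13.1% |

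The 240-per-arm column is from 20,000 runs per cell. Random pairing in those runs gives 5.0–5.2% throughout, so the excess comes from pairing by rank. The correlation of z with the chance imbalance in mean score is 0.25, 0.39, 0.47 and 0.63 down the rows.

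**Step 2: with the deletion rule.** Null simulation with 501 deletions, total about 485, 4,000 runs per cell (standard error about √(0.05 × 0.95/4000) = 0.3 points near 5%):

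| Arm difference | R² 0 | 0.1 | 0.2 | 0.3 | 0.5 |
|---|---|---|---|---|---|
| 1 | 4.7% | 4.9% | 6.5% | 6.8% | 11.8% |
| 5 | 3.3% | 3.7% | 4.7% | 5.8% | 10.4% |
| 10 | 2.5% | 2.9% | 5.1% | 5.1% | 9.9% |
| 20 | 2.1% | 2.6% | 3.2% | 4.8% | 8.7% |

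A separate simulation gave 4.0% and 11.5% (R² 0 and 0.5) for arms of 243/242, and 1.6% and 9.9% for 255/230. Where the level is near 5%, that is because two errors happen to offset.

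**Step 3: is it overfitting of the score?** Runs that fitted a section 13.2-type score in-sample (14 parameters, 101 deletions, 243/242) gave 7.0% at concordance 0.69 and 11.6% at 0.76. In a latent-normal model R² of 0.3 and 0.5 correspond to concordance of about 0.69 and 0.75, so this agrees with Step 2. Using the true linear predictor instead of the fitted score gave similar sizes. Rank pairing is the cause.

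**Step 4: does the remedy hold its level?** At 240 per arm (2,000 runs; R² 0.1, 0.2, 0.3, 0.5), a re-randomization p-value with re-pairing gave 5.7, 4.6, 5.1 and 5.2%. All-pairs comparison within pooled risk quintiles gave 5.4, 5.0, 5.1 and 5.6%. The rank-paired binomial test in the same runs gave 7.0, 6.7, 8.4 and 13.5%. The re-randomization check did not include the deletion step, and a resampling CI was not simulated.

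**The case against.** The strongest reply has four parts.

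1. **The formula is not in the SAP.** This stands. The binomial variance is the natural partner of the Step 3 proportion, but it is an assumption.

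2. **Chance imbalance enters every test that does not adjust for the score.** This is true, and it averages to zero over randomizations. A reader might infer that the method counts imbalance as treatment effect or favours one arm; nothing in the documents supports that. The defect is narrower. Random pairing and unadjusted all-pairs comparison face the same imbalance, but their variances include it, and they keep close to 5%.

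3. **Large errors need a very strong score.** This also stands. The fitted-score simulation reached 20.3% at concordance 0.82 (R² about 0.7), and it is tempting to quote that as the false-positive rate. The documents give no such strength, and section 13.2 fits the score to a Day 5 outcome, not to the 90-day comparison. With R² up to 0.3 and arms differing by 5 or more, size is about 2–6%.

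4. **The analysis is supplementary.** Section 8.2 adds it to separate recovery and death analyses, and it has no allocated alpha, gatekeeping role or stopping role. This limits the consequence. It does not make the printed CI correct.

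**Conclusion.** The point holds as a miscalibration. Assuming a pair-level binomial variance, the stated CI and p-value do not describe the estimator in section 8.2. The true level of a nominal 5% test runs from about 2% (weak score, clearly unequal arms) to about 12% (R² 0.5, nearly equal arms). The score's prognostic strength and the MP0420 arm split decide where it falls, and neither is documented. A reader might conclude that this trial's win-ratio test is anti-conservative; the documents do not settle whether it is liberal, conservative or close to nominal. Nor do they support reading this as bias toward MP0420 or control, or as a threat to the primary Gray's test.

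The size estimates rest on the borrowed AZD7442 outcome mix, a latent-normal model, and no loss to follow-up or site effects.

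**What to change.** In SAP section 8.2, keep the matched-pair point estimate and change the inference:

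- **p-value:** re-randomize arm labels within the randomization strata, repeat the full rank, pair, delete and median procedure each time, and compare the observed statistic with that distribution. The score is fitted to pooled data with no treatment term, so it need not be refitted when labels change.
- **CI:** use a resampling variance of that same whole procedure.
- **Wording:** print the formula used, and say whether the reported quantity is wins/(wins + losses), null 0.5, or wins/losses, null 1. Step 3 defines the first under the name of the second.

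A win ratio comparing all pairs within strata of the pooled, arm-blind score, with a U-statistic variance, could be added as an alternative or sensitivity analysis. It also avoids the random deletions. Making it the main method is partly a matter of preference, because it changes the prespecified statistic.

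Cost: SAP wording, modest programming and computing time. No new data are needed.

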1. At home for 14+ days (reached the primary endpoint of sustained recovery) *Did not reach sustained recovery, and:*

- 2. At home, < 14 days
- 3. Discharged from the hospital, but not at home
- 4. Hospitalized
- 5. Dead
- 6. Primary endpoint status unknown.

The proportions of participants in each of the 6 categories will be summarized over time, by treatment group (stacked bar graphs and tables). In this analysis, both "sustained recovery" and "death" are absorbing states.

Assessment of model assumptions

The trial was powered to detect an RRR of 1.25 with 90% power; this requires 843 sustained recoveries among the 1000 participants by Day 90. The rate of recoveries will be monitored, overall and within the two disease severity strata. Deviations of the observed distribution from the hypothesized distribution in the control arm will be monitored, and the impact on the power of the trial will be assessed. Prior to the completion of the trial for the investigational agent, sample size will be re-estimated by the blinded statisticians on the study team, based on the pooled rate of *sustained recovery*.

• The Fine-Gray model assumes that the sub-distribution rate ratio for *sustained recovery* is constant over time, similar to Cox proportional hazards models. The assumption of constant RRR will be tested by including an interaction effect between time and treatment indicator.

Sensitivity Analyses

- As sensitivity analyses, the primary comparison will be repeated after excluding participants who did not receive any of the investigational agent/placebo (modified intention-to-treat).
- Sensitivity analyses for the primary endpoint comparisons will include consideration of home oxygen above pre-morbid oxygen use (described in section 4.2.2 item 12 of the protocol). For these sensitivity analyses, *sustained recovery* will be re-defined as:
 - a. "Discharged to home, alive at home without use of continuous supplemental oxygen for an uninterrupted 14 day period"
 - b. "Discharged to home, alive at home for an uninterrupted 14 day period, and no supplemental oxygen use a the end of the 14 day period"
- If the RRR is not constant (test described under "assessment of model assumptions" above), as a sensitivity analysis, the RRR will be estimated within time periods, for example, Day 14-28, Day 29-60, Day 61-90.
- Additional sensitivity analyses are described under "censoring" above.

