8.3 Other Secondary Outcomes

The protocol defines a number of secondary endpoints in addition to the two key endpoints described in section 8.2 above. These analyses will be carried out for the final report. Selected secondary endpoints may also be analyzed for interim monitoring reports, to help evaluate the safety and efficacy of the investigational agent.

Below, the secondary outcomes from section 4.2.2 of the protocol are cited, with a short description of the analysis methods. For each outcome, the treatment group comparisons will be stratified by disease severity at study entry and by site pharmacy, as described in section 3 under "stratification".

- Time to discharge for the initial hospitalization. Treatment groups will be compared using time-to-event methods that take into account the competing risk of death, similar to the analyses for time to sustained recovery described in section 8.1.
 - Hospital readmissions will be summarized using methods for recurrent events (i.e. those who are readmitted will re-enter the risk set).⁹
- Days alive outside of a short-term acute care hospital up to day 90. For this analysis, the "last-off" method will be used, i.e., days from the latest hospital discharge to day 90 will be counted. A person who dies within 90 days will be assigned a value of 0, consistent with the approach taken in trials of intensive care-based interventions. We will present

the median days by group and test the hypothesis of no difference between arms with a Wilcoxon rank sum test.

- For interim analyses, only participants who have reached Day 90 (administrative follow-up for those who died) will be included, to avoid bias. Alternatively, a shorter time period may be used.
- Pulmonary+ and pulmonary ordinal outcomes on Days 1-7, and the pulmonary ordinal outcome on Days 14 and 28. The proportion of participants in each category of the pulmonary and pulmonary+ outcomes will be summarized over time (both outcomes at days 1-7, the pulmonary outcome also at Days 14 and 28); at each of those days, treatment groups will be compared using proportional odds models as described in section 3; the proportional odds models will be adjusted for the categories of the pulmonary+ outcome at baseline and for study site pharmacy. If participants in both disease severity strata are enrolled, the models will also be adjusted for the interaction between disease severity stratum and pharmacy.

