The event target and sample size for AZD7442 was increased on August 19, 2021 with a letter of amendment. This increase was based on the results of other trials (the RECOVERY trial and the ACTIV-3/TICO trials of bamlanivimab, VIR-7831 and BRII-196/198) and utilized pooled outcome data for AZD7442 to estimate the revised sample size. The new event target for the AZD7442 trial was 1,228. It was estimated that extending enrolment to September 30, 2021 would achieve a sample size of 1,500 participants, which was estimated to be required to achieve the event target of 1,228. With this event target a RRR of 1.20 could be detected with 90% power at the 0.05 (2-sided) level of significance. It also provided 90% power to detect a RRR of 1.28 for the subgroup of participants who are seronegative for neutralizing SARS-CoV-2 antibodies (nAb) at study entry (see Letter of Amendment of 19 August 2021).

E-3 Power Estimation Prior to Unblinding

On December 28, 2021, prior to unblinding any treatment comparisons for the trial of AZD7442, power was re-assessed based on updated pooled (AZD7442 and placebo groups combined) primary endpoint results. Pooled primary outcome data on December 28, 2021 are given in the table below.

	1455 Participants Randomized						
	1417 Infused and 38 not infused (35 withdrew consent)						
	nAb negative	nAb positive	Specimen not yet analyzed	Specimen not available	TOTAL		
Recovery status through Day 90	N=616	N=657	N=107	N=37	N=1417		
Withdrew prior to recovery	2	4	0	0	6		
Day 90 window closed and recovery status unknown	17	5	0	1	23		
Day 90 window not yet closed* and recovery status unknown	0	1	3	0	4		
Achieved sustained recovery	508	586	76	25	1195		
Home < 14 days	7	5	0	0	12		
Discharged from hospital, but not home	9	3	0	2	14		
Hospitalized	12	10	2	1	25		
Died before recovery	61	43	26	8	138		

 Table E-1. Recovery status of participants in the AZD7442 trial as of December 28, 2021

* The Day 90 window extends to Day 100.

The mITT study population included 1417 participants. At this time, most of the 90-day followup was completed. The last patient was randomized on September 30, 2021 and the visit window for the Day 90 visit extends to 100 days (January 8, 2022).

Overall, the number of primary events was 1,195, 33 events less than the target of 1,228. As the table below indicates, this does not have a material effect on power.

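### SAP section 8.2, Step 3, defines the win ratio as wins over wins plus losses, which is a win proportion (null 0.5, maximum 1)

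*SAP*

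**What the plan says.** SAP section 8.2 supplements the separate analyses of death and sustained recovery with a joint analysis by matched pairs. Participants are ranked by risk score within each arm and paired by rank. Each pair is classified for group A, the investigational agent, as a win, a loss or neither, first on death and then on recovery. Step 3 then gives the estimate explicitly, as the "number of wins in group A divided by the total number of pairs with a win or a loss in group A". For inference it says only "Calculate the 95% CI for the win ratio and p-value as described in" the cited methods paper.

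When the arms differ in size, the surplus participants are deleted at random 501 times. The data set with the median win ratio is kept, and "the final values of the win ratio, 95% CI and p-value are those calculated from this data set". The name therefore carries through to the reported result.

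Section 8.3 introduces the remaining secondary outcomes as "in addition to the two key endpoints described in section 8.2 above", so this analysis has key secondary status. Appendix G, which holds the MP0420-specific modifications, leaves the formula alone.

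**The concern.** The name and the formula in Step 3 describe different quantities. Pairs with neither a win nor a loss drop out, so the denominator is wins plus losses, and no natural reading of the sentence makes it losses alone. The result is a proportion between 0 and 1, centred on 0.5. The label suggests a ratio centred on 1.

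The SAP's other effect ratios have null value 1. Section 8.1 has recovery rate ratios above 1 favouring the agent, section 10.2.2 does the same for odds ratios, and section 9.2 reads hazard ratios below 1 as favouring active treatment. A value of 0.56 labelled a win ratio and placed beside these would naturally be read as unfavourable. Under the Step 3 formula the value stays below 1 however effective the agent is, unless it has no losses at all.

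The interval is a second risk. Its method is delegated to a paper that is not among the documents. If that method works on the wins-to-losses scale, the Step 3 estimate and its interval would be on different scales.

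**Working it through.** **Plan's own figure.** The SAP gives no assumed value, power or sample size for the win ratio, so there is no figure to reproduce.

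**Algebra.** Let W and L be the wins and losses for group A.

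- Step 3 as written: P = W/(W+L), with range 0 to 1 and P = 0.5 when W = L.
- Ratio of wins to losses: R = W/L, with range 0 upwards and R = 1 when W = L.
- Link: P = R/(1+R) and R = P/(1−P). P depends on R alone and not on the number of decisive pairs. P = 1 only if L = 0.

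| R = W/L | Step 3 value, R/(1+R) |
|---|---|
| 0.80 | 0.80/1.80 = 0.444 |
| 1.00 | 1.00/2.00 = 0.500 |
| 1.25 | 1.25/2.25 = 0.556 |
| 1.40 | 1.40/2.40 = 0.583 |
| 2.00 | 2.00/3.00 = 0.667 |
| 3.00 | 3.00/4.00 = 0.750 |

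**Worked example with an interval.** The counts are assumed: 120 wins and 80 losses. Appendix G reports 485 infused participants, so there can be at most 242 pairs, and 200 decisive pairs is possible.

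- P = 120/200 = 0.600. Standard error = √(0.6 × 0.4/200) = 0.0346. Wald 95% CI 0.532 to 0.668.
- R = 120/80 = 1.50. Transforming the limits by P/(1−P) gives 1.14 to 2.01.
- Test of equal wins and losses: z = (0.600 − 0.500)/√(0.25/200) = 2.83, two-sided p = 0.005. Testing P = 0.5 is the same as testing R = 1.

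On the Step 3 scale, a clear benefit appears as a so-called win ratio of 0.60 with its whole interval below 1. If the interval came from a method on the wins-to-losses scale, the report would show an estimate of 0.60 with limits 1.14 and 2.01, and the estimate would lie outside its own interval.

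**Median of the 501 repeats.** P/(1−P) increases with P, so the repeats rank the same on either scale and the same data set is chosen.

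**Illustration at the design effect.** Section 8.1 states: "The trial was powered to detect an RRR of 1.25 with 90% power". A simulation of the win and loss rules used 242 pairs and 4,000 replicates per setting. Pooled recovery was 1195/1417 = 84.3% and death before recovery 138/1417 = 9.7%. Both come from Table E-1 for AZD7442, so using them for MP0420 is an assumption. The median recovery day is not in the documents and was set at 19, 22 and 28.

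- RRR 1.25: W/L = 1.25, Step 3 value 0.555 to 0.556.
- RRR 0.80: W/L = 0.79 to 0.80, Step 3 value 0.442 to 0.445.
- Mean decisive pairs in these two settings and under no effect: 228 to 237 of 242.

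Benefit and harm of this size both give values below 1.

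**The case against.** The strongest reply is that the method is taken from a cited paper, which may supply both the conversion and the null value, and that the documents contain only one definition, explicit and reproducible. On this view the problem is a label. The two scales are one-to-one, so any reader can convert the result. The direction is clear because A is the investigational agent. The analysis is supplementary, with no power calculation, share of alpha or place in a testing order in sections 8.2 and 8.3, so no decision turns on it.

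Much of this stands. No claim is made here about which scale the paper uses, and the mismatch between estimate and interval is conditional on it. The p-value is unaffected provided that it tests equal wins and losses. The citation does not cure the defect, however. The SAP writes out its own formula for the estimate and, within Step 3, delegates only the interval and p-value. A programmer who saw the problem would have to depart from the written formula to correct it.

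The simulation can also be criticised. It pairs at random rather than by risk score, omits deaths after recovery, assumes no censoring before Day 90, assumes gamma-distributed death times with a mean of about 20 days, and borrows another agent's pooled outcomes. Those criticisms are fair, but the conclusion rests on the algebra and would be the same without the simulation.

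**Conclusion.** The concern holds. Step 3 defines a win proportion and calls it a win ratio, and neither section 8.2 nor Appendix G converts it or gives a null value. A true wins-to-losses ratio R is reported as R/(1+R), so 1.25 becomes 0.556. This is exact and needs no assumption about event rates, pairing or sample size.

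The consequence is confined to the point estimate of a key secondary analysis, its label, and the scale and reading of its interval. The choice among the 501 repeats, the primary analysis and the monitoring boundaries are untouched. It should be corrected because a favourable result could be published in a form that reads as unfavourable.

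**What to change.** Choose one of two wordings for Step 3 and use it throughout section 8.2.

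1. Define the win ratio as the number of wins in group A divided by the number of losses in group A, with null value 1 and values above 1 favouring the investigational agent. Report the 95% CI from the cited method on that same scale.
2. Keep the present formula, rename the estimate a win proportion wherever it appears, state the null value 0.5, and report the CI on the proportion scale.

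The first keeps the existing name and matches the direction and null value of the recovery rate ratio. Either costs one sentence in the SAP and one line of code, with renaming of the label under the second. No new data are needed, and the selected matched data set and the test of equal wins and losses do not change.
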